NHS guidelines recommend that all patients with acute traumatic brain injury (TBI) should be treated within a specialist neuroscience centre. Despite these guidelines, many patients are not. Reasons for this may include initial location post-trauma, bed availability, and local variation partly due to the clinical assessment of the severity of the TBI and likely prognosis for the patient. Although the guidelines are based on the best available research evidence, this research is not sufficiently robust and is only partly based on data from the UK. For example, the question as to what level of severity of TBI warrants transfer (patients may be either not severe enough, or too severe, to warrant transfer) has not been fully addressed. An accurate risk prediction model, validated on a large number of NHS patients with TBI, could be used both to provide sufficient robust evidence to address this issue and to ensure standard clinical assessment of severity.

This project addresses these two objectives: to validate risk models for TBI and to compare the outcomes and costs of care for patients by location of definitive critical care. The project consists of four phases:

Phase I (months 1-4): A systematic review will be used to identify suitable risk models and the data required for their application.

Phase II (months 5-29): A prospective cohort study will be undertaken in neurocritical care units, general critical care units within a neuroscience centre, and general critical care units outside a neuroscience centre to collect data on consecutive adult patients admitted following TBI.

Phase III (months 25-32): The risk models will be validated in the study data, and the strengths and weaknesses of each model will be assessed. If required, the risk models will be recalibrated.

Phase IV (months 19-36): The cost-effectiveness of managing patients with TBI in different critical care settings will be evaluated in an economic model.

RESEARCH OBJECTIVES

The primary aims of this work are to validate risk prediction models for acute TBI in the setting of neurocritical care in the NHS, and to use these models to evaluate the optimum location and comparative costs of neurocritical care in the NHS.

Specific, detailed objectives to achieve these aims are:

1. To identify, from the literature, the existing risk prediction models for acute TBI that are most likely to be applicable to a neurocritical care setting, and identify a full list of variables required in order to be able to calculate these models.
2. To collect complete, valid and reliable data for the variables identified above for consecutive adult admissions with TBI to dedicated neurocritical care units within a neuroscience centre, general critical care units within a neuroscience centre and general critical care units outside a neuroscience centre within the NHS.
3. To undertake a prospective, external validation of existing models for adult patients with TBI admitted to critical care, to identify the strengths and weaknesses of each model, and, if possible, to identify the best model to use for risk adjustment in this setting.
4. To describe and compare adjusted outcomes for adult admissions with TBI from dedicated neurocritical care units within a neuroscience centre, general critical care units within a neuroscience centre and general critical care units outside a neuroscience centre within the NHS.
5. To compare the cost-effectiveness of care for patients with TBI between dedicated neurocritical care units within a neuroscience centre, general critical care units within a neuroscience centre and general critical care units outside a neuroscience centre within the NHS.
6. To make recommendations for policy and practice within the NHS.

BACKGROUND

Risk prediction in adult, general critical care

Risk prediction models have been established in use in adult, general critical care units for over 25 years, since the publication of the original Acute Physiology And Chronic Health Evaluation (APACHE) model in 1981.¹ In the UK, the first large-scale validation of a risk prediction model was the Intensive Care Society's APACHE II Study in Britain and Ireland (1987–1989).^{2;3} This study produced recalibrated coefficients for the APACHE II model, and led, in 1994, to the formation of the Intensive Care National Audit & Research Centre (ICNARC) and the Case Mix Programme, the national comparative audit of patient outcome in adult, general critical care units in England, Wales and Northern Ireland. ICNARC has continued to pioneer developments in risk prediction in the Case Mix Programme, most recently through the validation and recalibration of a number of general risk prediction models⁴ and subsequent development of a new model, the ICNARC model.⁵

Risk prediction in neurocritical care – why not use a general model?

Unlike adult, general critical care, no data are routinely collected in the NHS for risk-adjusted comparison of outcomes from neurocritical care. Consequently, four dedicated neurocritical care units currently participate in the Case Mix Programme. However, there are significant limitations to using models developed and validated for general critical care for patients receiving neurocritical care. Using a spectrum of measures for calibration and discrimination, risk prediction models, successfully developed and validated for adult admissions to general critical care units showed significant departure from perfect calibration in admissions with head injuries to adult, general and dedicated neurocritical care units.⁶ The inclusion and handling of variables of specific prognostic importance in TBI is often poor.⁶ For example, the APACHE II model assumes that any patient that is sedated for the entire first 24 hours in the critical care unit is deemed neurologically normal, which has previously led to suggestions that pre-sedation values of the Glasgow Coma Scale (GCS) should be used for these patients.⁷ The only general model to take any account of changes detected on computed tomography (CT) scan is the Mortality Prediction Model (MPM) II, and the inclusion of CT information in this model is limited to the presence of an intracranial mass effect. Furthermore, all risk prediction models for adult, general

critical care use an outcome of mortality at discharge from acute hospital, which is not considered adequate for neurocritical care where longer term (e.g. six-month) mortality and morbidity are more valid outcomes.⁸

Risk prediction in traumatic brain injury

A number of specific models for TBI exist, however a recent systematic review by the Cochrane Injuries Group found that most models are limited by being based on small samples of patients, having poor methodology, and rarely being validated on external populations.⁹ Of 102 models for TBI identified in the review, only two models by Hukkelhoven et al¹⁰ (one for mortality and one for unfavourable outcome at six months) met minimal criteria of being developed using appropriate methods on data from at least 500 patients in multiple centres, and validated in an external population. These models were based on 2,269 patients with moderate or severe TBI ($GCS \leq 12$) enrolled in two randomised controlled trials (RCTs), one in the United States and Canada and the other in Europe, Israel and Australia. The model for unfavourable outcome at six months was validated in an observational database of 796 patients with moderate or severe TBI in 55 European countries from the core data survey of the European Brain Injury Consortium (EBIC). The model for six-month mortality was validated in the EBIC data and also in an observational database of 746 patients with non-penetrating severe TBI ($GCS \leq 8$) in four US centres from the Trauma Coma Data Bank (TCDB).

The authors of the systematic review have also gone on to develop new models for 14-day mortality and unfavourable outcomes at six months aimed at addressing the shortcomings identified in their review.¹¹ Separate models were derived using only 'basic' (demographic and clinical) variables and incorporating additional CT variables, and different models were reported for high-income countries and for low- and middle-income countries. These models were based on 10,008 patients with TBI ($GCS \leq 14$) in the Corticosteroid Randomisation After Significant Head injury (CRASH) RCT.^{12;13} Of these, 2,482 patients were recruited from high-income countries, including 1,391 patients from 45 centres in the UK. The models were validated in the International Mission for Prognosis And Clinical Trial (IMPACT) database,^{14;15} a database combining data from 9,205 patients with moderate or severe TBI from eight RCTs and three observational studies (including the development and validation data

from the Hukkelhoven models). The authors acknowledge that “further prospective validation in independent cohorts is needed to strengthen the generalisability of the models.”

Further models for TBI have recently been developed using the IMPACT database and validated in CRASH data.¹⁶ Three models of increasing complexity were presented for both mortality and unfavourable outcome at 6 months. The ‘core’ model consists of weights for age, GCS motor score and pupil reactivity. The ‘extended’ model additionally incorporates hypoxia, hypotension, CT classification, traumatic subarachnoid haemorrhage and epidural haematoma. Finally, the ‘lab’ model also incorporates weights for glucose and haemoglobin.

While these recent developments in risk prediction models for TBI indicate potentially significant improvements over previously available models, these models still have limitations regarding their external validity (generalisability) for use in evaluating neurocritical care of patients with TBI in the NHS.¹⁷ All these models were developed using some or all data from RCTs. Even when trials are pragmatic, as was the case for the CRASH trial, using data from an RCT to develop a prognostic model may impact on generalisability through self-selection of centres to participate in the trial, selection of patients enrolled in the trial, and the potential for all patients enrolled in a trial (in both active and control arms) to receive a better standard of care than usual.¹⁸ Much of the data used in developing and validating these models is old. Only the CRASH database contains data from within the last 10 years, with the Hukkelhoven models based on data from the early 1990s, and the IMPACT data collected between 1984 and 1997. Models based on data from multiple sources are limited by differences in definitions of variables, timings of measurements, and inclusion criteria between the different data sources. The CRASH models for high-income countries are clearly of the most direct relevance to UK practice, as over half of all patients recruited to CRASH from high-income countries came from centres in the UK. However, in the CRASH trial as a whole, only 50% of patients were admitted to critical care.¹² This figure may have been higher within the UK but, nonetheless, applying these models to a critical care setting may introduce selection bias and invalidate the model’s accuracy. It is clear that all these models require further prospective validation, and potentially

recalibration, before they can be applied with confidence for research and audit in neurocritical care in the NHS.

Delivery of neurocritical care for traumatic brain injury in the NHS

In the NHS, adult patients with TBI are rarely managed by a single service; they are managed by a succession of services from first contact to definitive critical care, definitive critical care not always being provided in a dedicated neurocritical care unit. Despite guidelines recommending that all patients with severe TBI be treated within a neuroscience centre,¹⁹ many (particularly those without surgical lesions) are currently neither treated in nor transferred to one. A combination of geography, bed availability, local variation and clinical assessment of prognosis can often determine the location of definitive critical care for an adult patient with TBI. The Neurocritical Care Stakeholder Group, established to offer expert advice to Department of Health and Commissioners, indicated in their audit report that, within the NHS, only 67% of beds ring-fenced for neurocritical care were in dedicated neurocritical care units and that neurocritical care unit occupancy rates exceeded 90% (especially for Level 3 beds).²⁰ Most neurocritical care for adult patients with TBI was delivered either in dedicated neurocritical care units (42%) or in general critical care units within a neuroscience centre (35%). However, despite clear guidelines and the progressive regionalisation of neurosurgical care since 1948, 23% of patients with TBI were treated in general critical care units outside a neuroscience centre. Local critical care consultant opinion indicated at least 83% of these patients required transfer to a neuroscience centre. No data were available, or are routinely collected, within the NHS for risk-adjusted comparisons.

Where adult patients with TBI should be optimally treated is an important question for the NHS, both in terms of outcomes and costs. Belief and limited evidence has underpinned the establishment, and continuing expansion, of dedicated, neurocritical care facilities in the UK^{21;22} but no formal evaluation has been undertaken. Recent research has suggested benefit from managing severe head injury in specialist centres,²³ however this is acknowledged to be inconclusive due to lack of adjustment for all known confounders and the use of an unvalidated risk prediction model. It also does not address the issue of general versus specialist critical care units within neuroscience centres. Research is required to determine which location(s) for

neurocritical care are associated with improved outcomes for adult patients with TBI, particularly for those who do not require surgical intervention (external ventricular drain and/or craniotomy/craniectomy), a NICE recommendation for future research in their recently revised guideline.¹⁹ A key issue for policy-makers is whether the additional initial costs of more specialised care are justified by subsequent reductions in morbidity costs and/or improvements in patient outcomes. While conventional RCT methodology may be impractical in this setting, the presence of variation in the way services are organised and delivered can allow them to be compared using observational methods. This is only possible if a valid, reliable, appropriate and accurate risk prediction model exists.

At its inaugural meeting in February 2007, the newly formed Neurocritical Care Network (NCCNet), a network of units and staff providing neurocritical care to patients in both dedicated and general units, identified pursuing funding and establishing a risk prediction model to investigate and evaluate the location and outcomes of care for adult patients with TBI as their first, and top, priority. It was recognised that this aim could only be achieved through validation of an accurate risk prediction model for adult patients with TBI. The Society of British Neurological Surgeons, the Neuroanaesthesia Society of Great Britain and Ireland, the Intensive Care Society and the Association of British Neurologists, through the auspices of the Neurocritical Care Stakeholder Group, are all supportive of this.

STUDY DESIGN

The project will be divided into four phases, detailed below:

- Phase I: Identification of suitable models and definitions of dataset (objective 1; months 1–4)
- Phase II: Data collection and data validation (objective 2; months 5–29)
- Phase III: Validation of risk prediction models (objective 3; months 25–32)
- Phase IV: Evaluation of location of neurocritical care (objectives 4–6; months 19–36)

The flow of patients through the project is shown in Appendix 1.

Phase I: Identification of suitable models and definitions of dataset

The systematic review of prognostic models for TBI⁹ will be updated by applying the same search strategy as used by the Cochrane Injuries Group (Appendix 2) to identify any new publications since 2005 meeting the inclusion criteria. Experts in the field, including the CRASH and IMPACT groups, will be approached to identify additional work, published or ongoing, that may be of relevance. We already have established research links with individuals from both the CRASH and IMPACT investigators. The RAIN Steering Group will review the models identified from the published systematic review and updated searches to select the most appropriate models for validation in the neurocritical care setting. These are likely to include the CRASH models for high-income countries, and the Hukkelhoven and IMPACT models.

Once the models have been selected, a list of all data fields required to calculate the models will be extracted from the published descriptions of the models, together with definitions, where available, clarified with the model authors where necessary. Precise rules and definitions for the collection of these fields will be laid out in a data collection manual, and the technical requirements will be defined in a detailed dataset specification.

Phase II: Data collection and data validation

All 208 units participating in the Case Mix Programme and all critical care units in neuroscience centres (identified through NCCNet) will be invited to participate. For the units already participating in the Case Mix Programme, RAIN data collection will be piggybacked onto routine data collection. Neurocritical care units not participating may choose to join the Case Mix Programme, but this will not be a requirement of the study and RAIN data collection may be piggybacked onto routine data collection for the Department of Health mandated Critical Care Minimum Data Set (CCMDS).

Abstraction of prospective administrative and clinical data will be undertaken by data collectors trained to collect a dedicated core dataset for RAIN according to precise rules and definitions. Depending on local infrastructure, additional data will be collected either by web-based data entry or by modification of existing Case Mix Programme Version 3.0-compliant software to incorporate the additional fields required. As for Case Mix Programme data, all the additional data will undergo extensive validation, both locally and centrally, for completeness, illogicalities and inconsistencies.

Detailed data will be collected on consecutive patients with acute TBI (see: *Planned inclusion/exclusion criteria*). However, administrative and CCMDS data will be collected for all admissions to all participating units. Critical care data on TBI patients will be placed in the context of all TBI, including those not admitted to critical care, using data from the Trauma Audit & Research Network (TARN).

Data collected will cover administrative (e.g. NHS Number, dates and times) and socio-demographic factors and factors from pre-hospital, and the first and subsequent hospitals as well as factors at arrival to the definitive location for neurocritical care. Data items collected will include all those required to calculate the models selected from Phase I, including: mechanism, severity and timing of TBI and other injuries; CT scan classification (first/last prior to admission); components of and total GCS (pre-intubation/at admission); pupil reactions (first/worst); and physiological parameters (first/worst).

The experience from the CRASH trial suggests that adequate quality CT data can be obtained through reports generated at contributing centres, and this will be our

primary method by which imaging data will be recorded. However, we are aware that there have been concerns expressed in the past about the validity of such peripheral reporting in clinical trials. It is essential to know whether the data obtained from local reporting of CT images is adequate for accurate risk adjustment, since this will have significant implications on the practicability of using any particular predictive model. Data collectors will therefore be asked to record appropriate identifiers to allow us to access CT scans for review at a later date if required, and will be requested not to discard or destroy the films or digital imaging data for these patients until 5 years after entry into the study. We will obtain copies of the admission CT scans in a randomly selected sample of 10% of patients, weighted to include more patients from outside neuroscience centres, where patient throughput will be lower. Data collectors will be requested to send anonymised admission CT scans to Addenbrookes Hospital (Cambridge University Hospitals NHS Foundation Trust) using the Image Exchange Portal, where possible. These will be centrally viewed and assessed by Neurosciences Critical Care Consultants at Addenbrookes Hospital, and the reports generated will be compared to the corresponding submitted data to identify any systematic discrepancies. If significant discrepancies are identified, we will arrange systematic collection and central reporting of CT scans from all patients, subject to additional funding.

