The primary outcomes will be mortality and unfavourable outcome, defined as death, vegetative state or severe disability on Glasgow Outcome Scale (Extended), at six months following admission to critical care. The duration of follow-up has been restricted to six months for the purpose of this study as this is the primary endpoint of the existing risk prediction models, and to limit costs, however discussions with service user representatives indicate that longer-term outcomes may be important. Further list cleaning against the NHS Central Register will enable ongoing follow-up of mortality beyond six months. Secondary outcome measures will include six-month and lifetime costs and cost-effectiveness.

Proposed sample size

We performed a simulation study to assess the power to detect a difference in the c index (area under the receiver operating characteristic, ROC, curve) between two different risk prediction models applied to the same population. Simulations were based on the following assumptions: the rate of unfavourable outcomes in the population will be 40% (based on the observed rate of unfavourable outcomes in high income countries in the CRASH trial,¹¹ and consistent with the results of a regional audit in East Anglia³⁹); statistical tests will be based on a two-sided p-value of $P=0.05$; we wish to be able to detect, with 80% power, a 10% relative difference in c index from the value of 0.83 observed for the CRASH model in the development sample.¹¹ A total of 17,500 datasets were simulated at different sample sizes using a binormal model⁴⁰ and the empirical power was assessed at each sample size as the proportion of datasets in which a statistically significant difference was detected (see Appendix 3).

Based on these simulations, a sample size of 3100 patients will be required for model validation. To allow for 8% loss to follow-up (based on the observed follow-up rates from CRASH and RESCUEicp), we will aim to recruit 3400 patients.

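### Phase IV groups patients by definitive location without aligning group assignment and start of follow-up for transferred patients, which leaves the comparison open to survivor (immortal-time) bias

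*Protocol*

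**What the plan says.** The summary gives one of the project's two objectives as to "compare the outcomes and costs of care for patients by location of definitive critical care". Under *Delivery of neurocritical care for traumatic brain injury in the NHS*, the protocol says of these patients that "they are managed by a succession of services from first contact to definitive critical care", and that, along with geography, "bed availability, local variation and clinical assessment of prognosis can often determine the location of definitive critical care for an adult patient with TBI". On who is moved, the summary notes that "patients may be either not severe enough, or too severe, to warrant transfer".

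*Phase II* collects pre-hospital data and data from "the first and subsequent hospitals as well as factors at arrival to the definitive location for neurocritical care", together with NHS Number, dates and times. Several items are recorded at more than one point, for example first and worst pupil reactions and physiology.

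*Phase IV* evaluates location with multilevel logistic regression for six-month mortality and unfavourable outcome, adjusted for the chosen risk model and for unit-level factors. Multilevel models also serve the cost and cost-effectiveness comparisons. *Proposed outcome measures* sets the endpoint "at six months following admission to critical care".

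Objectives 4 and 5 and the Phase IV section compare three unit types without using the word definitive. The text at hand does not define the term. It does not say to which unit a transferred patient, or a patient who dies before transfer, is attributed, or which critical care admission starts the six months. It names no analysis by first unit, at a landmark, or with location as time-dependent. The patient-flow diagram (Appendix 1) is not visible.

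**The concern.** For a patient first admitted to a critical care unit outside a neuroscience centre, the definitive location is settled by a later event that the patient must live to reach. If such a patient dies before being moved, no specialist location was ever reached, and the death stays with the outside unit. If the patient survives and is moved, the later outcome counts for the centre. The outcome therefore helps to decide the group.

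A baseline risk score balances risk at entry. It cannot undo a rule under which early death itself settles the group. The multilevel structure does not address this either.

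This is the policy comparison of the project. The same grouping feeds the incremental net benefits, the lifetime extrapolation and the recommendations for the NHS, so a distortion in the six-month contrast passes through to all of them.

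**Working it through.** **1. The plan's own figures.** Evaluable patients and loss (*Proposed sample size*): 3100 / (1 − 0.08) = 3370, which agrees with the target of 3400 after rounding. Accrual over 18 months:

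- neurocritical care units: 12 × 8 × 18 = 1728
- general units within a centre: 13 × 6 × 18 = 1404
- general units outside: 30 × 0.5 × 18 = 270

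The total is 3402, with 3132 within centres and 270 outside (7.9%). The protocol gives no figure for the Phase IV contrast.

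**2. Set-up under no true effect.** Unfavourable outcome is 40% everywhere (the protocol's rate). Two inputs are assumptions: *t*, the share of first-outside patients destined for transfer, and *e*, the share of those who die before it. The definitive-outside group is held at 270, and only participating units supply transfers.

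- First-outside patients: M = 270 / [(1 − t) + t·e]
- Outside unfavourable: M·[(1 − t)·0.40 + t·e]
- Transferred: M·t·(1 − e), of whom M·t·(0.40 − e) are unfavourable
- Direct centre admissions: 3132 − transferred, at 40%

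**3. Worked case, t = 0.5, e = 0.05.** M = 270 / 0.525 = 514. Transferred = 244; early deaths = 12.9. Outside: 514.3 × 0.225 = 115.7, and 115.7 / 270 = 42.9%. Within centres: (2887.7 × 0.40 + 514.3 × 0.5 × 0.35) / 3132 = (1155.1 + 90.0) / 3132 = 39.8%. Odds ratio, outside v centre: 1.14.

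**4. Range of the spurious odds ratio.**

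| t | e = 1% | e = 3% | e = 5% | e = 10% |
|---|---|---|---|---|
| 20% | 1.01 | 1.02 | 1.03 | 1.07 |
| 50% | 1.03 | 1.08 | 1.14 | 1.27 |
| 80% | 1.11 | 1.33 | 1.56 | 2.13 |

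At t = 80%, e = 5% there are 45 early deaths, with 50.0% v 39.1% unfavourable.

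**5. Same null, time-aligned.** By first critical care unit, both groups are at 40% and the odds ratio is 1.00. At a landmark after the transfer window, if the same share e = 5% of every group has died by then, each group's risk among survivors is (0.40 − 0.05) / 0.95 = 36.8%, and the odds ratio is again 1.00.

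**6. Direction.** Keep t = 0.5 and e = 0.05, but let patients who are kept outside have a residual risk, not captured by the score, other than 40%. The odds ratio is 0.76 at 30%, 0.93 at 35%, 1.14 at 40% and 1.38 at 45%. Residual selection can cancel or reverse the survivor effect.

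**7. Scale against sampling error.** Ignoring clustering and loss to follow-up, the standard error of the log odds ratio is √[1/(270 × 0.24) + 1/(3132 × 0.24)] = √(0.01543 + 0.00133) = 0.129. The log of 1.14 is 0.131, so the bias in the worked case is about one standard error.

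**The case against.** **No rule is stated, and detail belongs elsewhere.** No sentence in the protocol says that deaths before transfer count as outside. Attribution of transfers and choice of index admission are often left to a statistical analysis plan, which the steering group is to approve, and the flow diagram cannot be seen. This stands in part: the attribution rule is undefined rather than wrongly stated. But the protocol itself fixes the grouping variable, and the survivor condition follows from that choice for anyone first admitted outside.

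**Direction.** A reader might infer that the comparison is biased, on balance, towards specialist care. The documents do not support that. The summary says patients may be too mild or too severe to move, and step 6 shows the net effect can go either way.

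**Reach.** A reader might take the problem to cover all patients and all early deaths. It does not. Direct admissions to a centre face no survival condition, and deaths before any critical care admission never enter the cohort.

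**Baseline.** A reader might infer that transferred patients will be scored on values taken after earlier treatment. This is not shown: arrival values are collected in addition to first-hospital values. What remains is that Phase IV does not say which set it will use.

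**Size.** Larger figures follow if transfers are taken to be 30–50% of the centre group. Suppose 5% of first-outside patients die before transfer is possible, half of the rest move, and later mortality is 20% everywhere. Then mortality is 27.6% outside and 22.8–22.0% inside, an odds ratio of 1.29–1.35. Planned accrual instead implies a transfer share of 244 / 3132 = 7.8%. Inside mortality is then 0.078 × 0.20 + 0.922 × 0.24 = 23.7%, an odds ratio of 1.23. Transfers from non-participating units would raise the share.

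**Clock.** For a binary six-month endpoint, a shifted start matters little by itself unless the interval before transfer is long, and no interval is given.

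**Conclusion.** The point holds as a structural weakness in the Phase IV comparison. Grouping by definitive location, without aligning assignment and follow-up for transferred patients, makes survival to transfer a condition of joining the specialist group for those first admitted to an outside critical care unit. That mechanism alone favours specialist units, and risk-score adjustment does not remove it.

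The net direction is not established. The spurious odds ratio runs from negligible (1.01) to large (2.13) over the assumed values. The result rests on those two assumed inputs, on a 40% outcome rate throughout, and on transfers arising only from participating units. Because the outside group is about 270 of 3402, some 13 early deaths move its rate from 40% to 42.9%.

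**What to change.** - Define definitive location, and state to which unit transferred patients and deaths before transfer are attributed.
- Keep one linked record per patient, using NHS Number.
- Start the six months at first critical care admission for everyone.
- Use the earliest (first-hospital) predictor values for everyone in the Phase IV adjustment.
- Alongside the definitive-location comparison, prespecify an analysis by first critical care unit (within participating units) and/or a landmark analysis with the landmark varied, reporting deaths before the landmark by first location.
- State that the conclusion on location will be tempered if these analyses disagree.

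The dates, times, identifiers and first-hospital factors are already to be collected, so the cost is mainly extra analysis. Deaths before the landmark leave the landmark contrast, so a single early landmark as the only primary analysis would change the question to one about survivors. Transfers from non-participating units need separate handling. None of these steps cures residual confounding by prognosis.
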